### **9.3.3 Efficacy Analyses across Subgroups**

The heterogeneity of treatment effects across age, sex, and ethnicity will be evaluated using a statistical test for interaction terms. Specifically, effects of treatment in subgroups will be determined by including the additional interaction terms between treatment and the three subgroups (age, sex, and ethnicity) in the repeated measures model described above for the eight efficacy variables.

The following variables will be treated as categorical variables in all of the linear mixed models.

- Treatment arms: CSI (reference), BMAC, ADP, UCT
- Age:  $\leq 65$  (reference) vs.  $>65$
- Sex: female vs male (reference)

- Ethnicity: Hispanic vs non-Hispanic
- Time: 0, 1, 2, 3, 4, 5 representing baseline and 1, 3, 6, 9 and 12 months follow-up visits

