#### **9.3.2 Primary and Secondary Efficacy Analyses**

Eight separate repeated-measures analysis will be performed on the eight efficacy variables described above. Each of the eight variables will be used as a dependent variable. The following model building method will be used for each analysis. Using Statistical Analysis System (SAS) MIXED Procedure (version 9.4; SAS Institute, Cary, NC), a linear mixed model will be fit on each efficacy variable. The model will include site, treatment arm, time on study (baseline and 1, 3, 6, 9

and 12 months on study), and treatment arm by time interaction as fixed effects. Subject ID will be the random effect. A compound-symmetric variance-covariance form in repeated measurements will be assumed and robust estimates of the standard errors of parameters will be used to perform statistical tests and construct 95% confidence intervals. The model-based means are unbiased with unbalanced and missing data, assuming missing data are non-informative. A P-value  $\leq 0.05$  will be considered statistically significant for all the terms in the mixed model. The statistical test for interaction between time on study and treatment will be the overall hypothesis test to determine whether efficacy variables in the four treatment arms changed significantly during 12 months of follow-up. If mean scores in the treatment arms are consistently different or similar over time (i.e., no statistical interaction) then the main effect test for treatment will be used as the primary hypothesis test to compare the treatment arms. The primary study results from this model will be the mean score and 95% confidence interval for each of the 4 treatment arms and the treatment mean differences and 95% confidence intervals.

Assuming a significant treatment effect on efficacy score change is identified (i.e., the interaction test is significant at  $P = 0.05$ ) then the six pairwise treatment comparisons on pain score change will be performed. A Bonferroni correction ( $p=0.05/6=0.0083$ ) for multiple comparisons will be applied. Specific statistical tests on efficacy score change will be done within the framework of the mixed effects linear model. All statistical tests will be 2-sided and adjusted for multiple comparisons. The same Bonferroni method will be used if the statistical interaction between treatment group and time on study is not significant but the main effect test for treatment is significant.

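### Section 9.3.3 tests subgroup interactions with uncorrected robust standard errors, which reject too often if a subgroup level, most plausibly in ethnicity, has few subjects per arm

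*Combined protocol and SAP*

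**What the plan says.** Section 9.3.3 says that "effects of treatment in subgroups will be determined by including the additional interaction terms between treatment and the three subgroups (age, sex, and ethnicity"). These terms go into the section 9.3.2 model, for each of the eight outcomes. The factor at issue is coded "Ethnicity: Hispanic vs non-Hispanic".

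The section 9.3.2 model has a compound-symmetric working covariance. On inference, the section says that "robust estimates of the standard errors of parameters will be used to perform statistical tests and construct 95% confidence intervals". A P-value of 0.05 or less "will be considered statistically significant for all the terms in the mixed model". The software is the SAS MIXED procedure.

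Section 9.3.2 also makes unknown ethnicity or gender a level of its own once it exceeds 5% of subjects. Section 9.2 plans 30 subjects per treatment group at each of four sites (120 per group, 480 in all) and expects 90% retention at one year.

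Section 9 gives no small-sample correction to the robust errors, no minimum cell size and no expected Hispanic share.

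**The concern.** A sandwich variance is built from squared residuals. With 120 subjects per arm it is close to right for the main treatment comparison. For a treatment-by-ethnicity term, its accuracy depends on the smallest ethnicity level within each arm. If that cell is small, the variance is biased low and poorly estimated, and an F test with hundreds of denominator degrees of freedom allows for neither.

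At stake is a false report that a cell product works differently in a minority group. The test is run on eight efficacy variables. Adjusting for the number of tests would not cure this, because each p-value from a sparse factor is already too small.

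**Working it through.** **1. The plan's own figures.** With n = 121 per group, the standard error of a difference is SD × √(2/121) = SD × 0.1286.
- VAS: 1.5 / (3.5 × 0.1286) = 3.33; two-sided 5% t-test power 91.3% (plan: 91%).
- Total KOOS: 10 / (20 × 0.1286) = 3.89; power 97.2% (plan: 97%).

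Both reproduce. For the subgroup tests the plan states only the 5% level.

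**2. Why small cells matter.** For the mean of m subjects in one cell, the uncorrected sandwich has expectation (σ²/m) × (m−1)/m. It is therefore low by 1/m: 17% at m = 6, 8% at m = 12, 4% at m = 24 and 0.8% at m = 120. The estimate also carries only about m−1 degrees of freedom.

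**3. Cell sizes.** Expected Hispanic subjects per arm = 120 × share: 6 at 5%, 12 at 10%, 24 at 20%. The unknown-level rule takes effect above 0.05 × 480 = 24 subjects, also about 6 per arm.

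**4. Rejection rate under no heterogeneity.** Inputs from the plan: 480 subjects, four arms, four sites, six visits, 10% dropout, compound symmetry. Assumptions: normal data, within-subject correlation 0.5, 25% over 65, 55% female, ordinary uncorrected sandwich. The model has site, arm, time, arm × time, the three factors and arm × each factor. The test is a 3-df F at 5%, with 2,000 to 4,000 simulated trials per row.

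| Hispanic share (assumed) | Expected per arm | Rejection, robust |
|---|---|---|
| 4% | 4.8 | 32% |
| 5% | 6 | 24-25% |
| 8% | 9.6 | 13% |
| 10% | 12 | 11% |
| 15% | 18 | 8-9% |
| 20% | 24 | 7% |
| 30% | 36 | 7% |

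- With counts held equal across arms: 16-17% at 6 per arm and 10% at 12 per arm.
- With serially decaying correlation: 22% at a 5% share and 11% at 10%.
- Coverage of the robust 95% interval for one treatment-by-Hispanic coefficient, from a separate simulation of the same design: 88.9%, 92.5% and 94.0% at shares of 5%, 10% and 20%.
- Arm-by-sex and arm-by-age tests in the same data: about 5-7%. Other runs with 15-25% over 65 gave up to about 8% for age.
- Model-based errors in the same data: 4.4-6.1% at every share from 2% to 30%. Here the fitted covariance is correct by construction.

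**5. Candidate remedies.** This is a simpler check: one value per subject, site + arm × ethnicity, no heterogeneity, 4,000 runs per row (simulation standard error about 0.3 points at 5%). Corrected means each residual is divided by one minus its leverage.

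| Hispanic SD relative to rest (assumed) | Share | Uncorrected | Corrected | Model-based |
|---|---|---|---|---|
| 1.00 | 5% | 23.6% | 12.4% | 5.3% |
| 1.00 | 10% | 10.3% | 6.2% | 4.8% |
| 1.00 | 20% | 7.1% | 5.6% | 5.4% |
| 1.25 | 5% | 23.5% | 12.0% | 15.1% |
| 1.25 | 10% | 10.5% | 6.6% | 14.1% |
| 1.25 | 20% | 6.4% | 4.7% | 10.7% |

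Keeping only trials with at least 10 Hispanic subjects in every arm, the corrected test rejects 4.9% (10% share) and 5.6% (20%) with equal SDs, and 6.2% and 4.7% with the ratio 1.25. Dividing residuals by the square root of one minus leverage is weaker: 8.0% at a 10% share with equal SDs.

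**6. How often the minimum would bind.** At a 10% share, P(Binomial(120, 0.10) ≤ 9) = 0.229 for one arm, so for at least one of four arms it is 1 − (1 − 0.229)⁴ = 0.65. At 15% it is about 0.04; at 5% it is practically certain.

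**The case against.** **The size depends on a share that the plan does not give.** This stands. A reader might infer that ethnicity cells will certainly be tiny and that a 10-25% error rate is a property of the plan. The documents do not support that: at a 15-20% share the rate is 7-9%. The direction is less fragile, since no share examined from 2% to 30% gave a robust ethnicity test below nominal.

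**Most of the subgroup analysis is sound.** This stands too. It would be tempting to say that all the subgroup interactions are invalid, but the sex test is near nominal and the age test only mildly inflated. It would also be tempting to cite the larger inflation expected if the interaction were carried across visits, but section 9.3.3 names interactions between treatment and the subgroups only, without time.

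**Robust errors serve a purpose.** Switching to model-based errors looks like the obvious cure, and under equal variances it is. If the Hispanic SD is 1.25 times the rest, however, those errors reject about 11-15% of the time. An unstructured covariance over visits does not help, because the problem is variance that differs between subgroups.

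**The stakes are limited.** Section 9 makes no decision on the subgroup tests. Section 9.3 also calls itself a summary of a statistical analysis plan whose separate text is not in the document reviewed, so a sparse-cell rule may exist there. The point concerns section 9 as written.

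**Conclusion.** The concern holds in a conditional form. As written, section 9.3.3 inherits robust standard errors with no small-sample correction. If 5-10% of subjects are Hispanic, the nominal 5% treatment-by-ethnicity test rejects about 10-25% of the time under no heterogeneity; at 20% it rejects about 7%. An unknown ethnicity or gender level just above 5% of subjects would give cells of the same size and so the same problem, although that case was not simulated separately.

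These figures assume the ordinary uncorrected sandwich, normal data and the correlation stated above. The primary treatment comparison is not affected. The change is worth making before analysis, but it is not an obstacle to the trial.

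**What to change.** In section 9.3.3, state that:

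1. Subgroup interaction tests and intervals use robust standard errors with a leverage (bias) correction. Name the form; the one that worked here divides each subject's residuals by one minus their leverage.
2. Any subgroup factor with a level, including an unknown level, below about 10 subjects in any arm is reported descriptively, without an interaction test. Both parts are needed: at a 5% share the correction alone still leaves about 12%.
3. Model-based standard errors with Kenward-Roger degrees of freedom may be given as a sensitivity analysis, not as the sole replacement.

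The cost is two or three sentences, a little extra programming and slightly wider subgroup intervals. The real loss is that there may be no formal ethnicity test: with a minimum of 10, it would be dropped in about 65% of trials at a 10% Hispanic share and in about 4% at 15%. The threshold is a judgement and can be set once the blinded, pooled ethnicity counts are known. Nothing in section 9.3.2 needs to change for the primary comparison on this account.

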Eligibility Criteria	
Inclusion Criteria:
 
 
1. Age <math>\geq 40</math> but <math>\leq 70</math> years old
 
2. Males and Females
 
3. Recent knee radiograph of the targeted knee (Standing AP lateral and sunrise view)
 
4. Diagnosis of OA in the targeted knee (radiographic evidence of OA in the medial and/or lateral tibiofemoral compartment, which would include one or more osteophytes on a standard radiograph taken within 3 months). Subjects may have concomitant patellofemoral but must have grade II or higher medial or lateral tibiofemoral knee OA and the primary pain must be related to tibiofemoral arthritis.
 
5. Continued OA pain in the targeted knee despite conservative measures (per treating provider's discretion)
 
6. Average daily VAS <math>\geq 3</math>
 
7. Kellgren-Lawrence system of Grade II, III, or IV
 
8. Females of childbearing potential (FCBP) only, must have a negative pregnancy test done at screening prior to enrollment. FCBP is defined as any premenopausal female unless they have had a surgical sterilization procedure such as, but not limited to, hysterectomy, oophorectomy, or tubal ligation
 
9. Women and men of child-producing potential must agree to use acceptable contraception methods for the duration of the trial such as birth control pills or condoms with spermicide
 

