### **6.2.2 Implementation of Randomization and Blinding**

Subjects randomized to Arm 1 or Arm 2 will undergo a procedure (bone marrow aspiration or liposuction) but will only receive one of the possible injections. For instance, subjects randomized to the control portion of Arm 1 will undergo a bone marrow aspiration but will receive a blinded corticosteroid injection. The bone marrow aspirate will still be processed and used to help quantify cell characteristics. Subjects randomized to Arm 3 will not undergo the procedures mentioned above. They will be blinded and receive either the stem cell injection or the corticosteroid injection.

Four hundred eighty subjects will be randomly assigned to treatment in this multicenter trial. Subjects at each clinical site will be randomized to ensure the trial is single-blind with a 1:1 allocation ratio across the four treatment groups.

One hundred twenty subjects will be randomized at each of 4 clinical sites. Arm 1: Forty subjects will be randomized with a 3:1 allocation ratio (bone marrow derived MSCs versus corticosteroid injection; 30:10). This same implementation plan will be used to randomize 40 subjects to Arm 2 (adipose derived MSCs versus corticosteroid injection) with a 3:1 allocation ratio and to randomize 40 subjects to Arm 3 (umbilical cord tissue MSCs versus corticosteroid injection) with a 3:1 allocation ratio.

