#### **9.2 Sample Size Determination**

The total estimated sample size for the proposed intention-to treat, parallel-group, multicenter, randomized, controlled trial is 480 subjects. The primary endpoints are Visual Analog Scale (VAS) pain score and the pain subsection of the Knee Injury and Osteoarthritis Outcomes (KOOS). The sample size calculations are based on improvements (from baseline to 1-year) in the visual analog scale (VAS) pain score and total KOOS. Total KOOS was used as a proxy and should ensure that the study is amply powered.

Assuming a decline of 1 point on average in pain in the Control arm (corticosteroids) and a decline on average of 2.5 points in a treatment arm (mesenchymal stem cells) and an estimated standard deviation on change of 3.5, the proposed sample sizes (n=121 subjects

per group or 484 total subjects) will provide 91% power to detect a difference on change of 1.5 points at the two-sided 5% significance level if the true difference between treatment groups is 1.5 points (two-sided two-sample equal variance t-test).

Assuming an increase of 10 points on average in total KOOS in the Control arm (corticosteroids) and an increase on average of 20 points in a treatment arm (mesenchymal stem cells) and an estimated standard deviation on change of 20, the proposed sample sizes (n=121 subjects per group or 484 total subjects) will provide 97% power to detect a difference on change of 10 points at the two-sided 5% significance level if the true difference between treatment groups is 10 points (two-sided two-sample equal variance t-test).

Each of the four participating sites will accrue 30 subjects to each of the 4 treatment groups. Cohort retention is expected to be 90% at 1-year.

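### The treatment-by-age test cuts age at 65 in a population limited to 40 to 70, so it detects a gradual age effect less efficiently than the exact age would

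*Combined protocol and SAP*

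**What the plan says.** Section 9.3.3 of the combined protocol and SAP states: "The heterogeneity of treatment effects across age, sex, and ethnicity will be evaluated using a statistical test for interaction terms". The terms are added to the repeated-measures model of section 9.3.2 for each of the eight efficacy variables. The same section then lists codings, introduced by "The following variables will be treated as categorical variables in all of the linear mixed models". Age is on that list with two levels: 65 or below (the reference) and above 65.

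The synopsis (1.1) and section 5.1.1 restrict enrolment to ages 40 to 70 inclusive.

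Section 9.2 sets the group size: "Each of the four participating sites will accrue 30 subjects to each of the 4 treatment groups", which is 4 × 30 = 120 per group. It adds: "Cohort retention is expected to be 90% at 1-year".

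The documents give no expected age distribution, no expected number above 65, no reason for the cut, no power for the subgroup tests and no analysis of age on its original scale.

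**The concern.** The above-65 category spans ages 66 to 70 in whole years, while the reference category spans 40 to 65. A test on this split cannot see any change in treatment effect within the lower 26 ages, and its precision is governed by however many subjects fall in the top five. If the benefit of a cell product rises or falls gradually with age, the split is an inefficient way to look for it.

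At stake is the only evaluation of age heterogeneity that the protocol describes. A non-significant result could carry very little information. Exact age is needed for eligibility, so a finer analysis requires no new data.

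**Working it through.** **Inputs.** Age range 40 to 70 (5.1.1); cut at 65 (9.3.3); 120 per group, VAS change SD 3.5, planned VAS difference 1.5 points, two-sided 5% level (9.2). The age distribution is assumed.

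**1. The plan's own figures.** For n = 121 per group, a two-sample t-test with difference 1.5 and SD 3.5 has noncentrality 1.5 / (3.5 × √(2/121)) = 3.33 and power 91.3%. For KOOS, 10 / (20 × √(2/121)) = 3.89 and power 97.2%. Both agree with the stated 91% and 97%. They concern the main comparisons; nothing comparable is stated for the subgroup tests.

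**2. Age information kept, uniform whole-year ages.** For a linear gradient, the relative efficiency of the split is the squared correlation between age and the above-65 indicator:

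r² = p(1 − p) × (mean age above 65 − mean age at or below 65)² / variance of age

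- p = 5/31 = 0.161, or 19.4 of 120 per group
- The means are 68 and 52.5, a difference of 15.5
- Variance = (31² − 1)/12 = 80
- r² = (5/31)(26/31) × 15.5² / 80 = 0.406

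So about 41% is kept and 59% lost. The split would need 1/0.406 = 2.5 times the subjects to match a linear term. Treating age as a continuous uniform variable gives 3 × (5/6) × (1/6) = 0.417, practically the same.

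**3. Power of the split.** This is a simple approximation: one cell arm against corticosteroid, 1-year VAS change.

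SE of interaction = 3.5 × √(2/n_high + 2/n_low)

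- With 19.4 and 100.6 per group, SE = 1.23. For a 1.5-point interaction, z = 1.5/1.23 = 1.22 and power is about 23%. Rounding to 20 and 100 changes it by less than a point.
- The interaction detectable with 80% power is 2.80 × 1.23 = 3.4 points.
- With 90% retention (108 per group), SE grows by √(120/108) = 1.054, giving about 3.6 points.

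**4. The same gradient tested with continuous age.** A linear gradient that puts 1.5 points between the two category means has slope 1.5/15.5 = 0.097 points per year. Its SE is 3.5 × √(2/120) / √80 = 0.0505, so z = 1.92 and power is about 48%. That is roughly double, but still below 80%.

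**5. Other age distributions.** Normal ages truncated to whole years 40 to 70; parameters are before truncation. The last column uses the formula in step 3.

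| Assumed ages | Enrolled mean | Above 65, per 120 | Information kept | Power of split, 1.5 points |
|---|---|---|---|---|
| Normal 55, SD 6 | 55.0 | 4 | 17% | 9% |
| Normal 55, SD 8 | 55.0 | 9 | 26% | 14% |
| Uniform | 55.0 | 19 | 41% | 23% |
| Normal 60, SD 8 | 58.6 | 20 | 38% | 24% |
| Normal 62, SD 8 | 59.9 | 26 | 43% | 28% |
| Normal 65, SD 8 | 61.7 | 36 | 50% | 33% |
| Normal 65, SD 6 | 63.1 | 42 | 56% | 35% |

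**6. Reach.** Section 9.3.2 lists the terms of the main model: "The model will include site, treatment arm, time on study (baseline and 1, 3, 6, 9" and 12 months, plus arm by time. Age is not among them.

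**The case against.** The strongest case on the other side has four parts.

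- **The loss is not a known quantity.** A reader might infer that the cut throws away more than half of the age information and leaves a very small upper group. The documents do not support that as fact, because they give no age distribution. With an enrolled mean of about 62 or more the loss is half or less, and the upper group may be 36 to 42 per arm. Even with uniform ages, about 19 per arm (77 of 480) is better called small and unbalanced. This objection stands, so the size must be given as a range.
- **The efficiency argument presumes a gradient.** If the treatment effect changes abruptly at 65, the split loses nothing and a linear term is the weaker test. This also stands, although the documents offer no argument for such a step.
- **Little depends on it.** A prespecified two-group split is common, no power is claimed for subgroup tests, and no decision in the protocol rests on the age result. The sentence on categorical coding in all of the mixed models might suggest that the age split enters the primary analysis. It does not, as the term list in 9.3.2 shows. Nor do the documents say that a null test would be read as absence of an age effect; that is a risk of interpretation only. This limits the importance of the point but does not make the split the better method.
- **Section 9.3 calls itself a summary of a separate plan.** A continuous-age analysis might exist elsewhere. Even so, the rule stated here is the categorical one.

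**Conclusion.** The point holds as an inexpensive improvement to a subgroup analysis, not as a flaw in the main analyses. For a roughly linear age gradient, the cut at 65 keeps about 41% of the information under uniform ages and about 17% to 56% across truncated-normal ages with enrolled means of 55 to 63. The corresponding number above 65 is about 4 to 42 of 120 per group. Under a step at 65 there is no loss.

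The 23% power for a 1.5-point interaction assumes uniform ages, the protocol's SD of 3.5, full retention and a single pairwise contrast on 1-year change. The planned mixed-model interaction test is not identical to that contrast, so the figure indicates order of magnitude only. The primary and secondary treatment comparisons are unaffected.

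**What to change.** In section 9.3.3 and the SAP, prespecify age as a continuous variable in the treatment-by-age interaction test, with a spline term as a check for non-linearity. Keep the groups at or below 65 and above 65 only for displaying subgroup estimates with confidence intervals. State that the test has limited power, so that a non-significant result is not taken as evidence of a uniform effect.

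The cost is a few sentences of analysis wording, with no new data, visits or subjects. The change should be made before treatment codes are linked to outcomes, so that it does not look data-driven. The downside is the assumption of an approximately linear gradient, which the spline check addresses in part. Continuous age will not make the test well powered: under uniform ages the example above rises only from about 23% to about 48%.
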